8.1.2 SERIOUS ADVERSE EVENT (SAE)

An SAE is any AE occurring at any dose that:

- results in death;

- Is life threatening, defined as any event that places the subject at immediate risk of death from the event as it occurred. It does not include an event that, had it occurred in a more severe form, might have caused death;
- results in hospitalisation or prolongation of existing hospitalisation, excluding admission for social or administrative reasons;
 - Hospitalisation is defined as any inpatient admission (even if less than 24 hours) (unless it occurs to ensure treatment compliance). For chronic or long term inpatients, inpatient admission also includes transfer within the hospital to an acute/intensive care inpatient unit.
 - Prolongation of hospitalisation is defined as any extension of an inpatient hospitalisation beyond the stay anticipated/required in relation to the original reason for the initial admission, as determined by the investigator or treating physician.
 - Hospitalisation for a pre-planned or elective treatment/surgical procedure should not be reported as an SAE unless there are complications or sequelae which meet the criteria for seriousness described above.
- results in a persistent or significant disability/incapacity, where disability is a substantial disruption of a person's ability to conduct normal life functions;
- results in congenital anomaly/birth defect in the offspring of a subject who received the product;
- Is an important medical event that may not result in death, be life-threatening, or require hospitalisation but that when, based upon appropriate medical judgment, may jeopardise the subject and may require medical or surgical intervention to prevent one of the outcomes listed in this definition. Examples of such medical events include allergic bronchospasm requiring intensive treatment in an emergency room or at home, blood dyscrasias or convulsions that do not result in hospitalisation, or the development of product dependency or product abuse.

8.1.3 DEATH

All AEs resulting in death whilst using the medicinal product must be reported to Ipsen within 24 hours of the Investigator's knowledge of the event. All fatal outcomes should be considered as adverse events, even if this fatal outcome is not considered to be related to the medicinal product.

The convention for recording death on the adverse event reporting form is as follows:

- Adverse event term that led to death (e.g. multiple organ failure, pneumonia, myocardial infarction).
- Outcome: fatal.
- The only exception is if the cause of death is unknown (i.e. sudden or unexplained death), in which case the adverse event term may be 'Death' or 'Sudden death'.

8.1.4 SPECIAL SITUATIONS

This is any incidence of drug exposure during pregnancy or breast-feeding, overdose, off-label use, medication errors, occupational exposure, abuse, misuse or lack of therapeutic effectiveness whilst using the medicinal product. A 'special situation' should be collected by the Investigator and reported to Ipsen whether or not these 'special situations' are associated with an adverse event.

8.1.4.1 PREGNANCY

Pregnancy itself is not regarded as an adverse event unless there is a suspicion that the medicinal product has interfered with a contraceptive method. If pregnancy occurs whilst using the medicinal product, the outcome of the pregnancy will then need to be collected. This applies irrespective of whether the pregnancy is considered to be related to interference by the medicinal product with a contraceptive method.

Information regarding any pregnancies must be collected on the adverse event report form, including those with normal progress and outcome. The investigator must instruct all female subjects to inform them immediately should they become pregnant whilst using the study medication.

Reports of pregnancy must be reported to Ipsen within 24 hours of the Investigator's knowledge.

8.1.4.2 OVERDOSE

An overdose is any dose of the medicinal product given to a study participant that exceeds the dose described in the protocol. Overdoses are not considered AEs; however, all overdoses should be reported to Ipsen within 24 hours. An overdose should be reported even if it does not result in an AE.

8.2 COLLECTION AND REPORTING OF ADVERSE EVENTS, FATAL OUTCOMES AND SPECIAL SITUATIONS

| Note |
|--|
| From this point onwards, the term 'Safety Report' will collectively refer to all reports of AE, fatal outcomes and special situations. |

8.2.1 COLLECTION OF SAFETY REPORTS

All safety reports, whether they are serious/non-serious, related/unrelated, should be collected by the Investigator in the study source document during the course of the study.

The Investigator must report all safety reports on the Clinical Study Serious Adverse Event (SAE) report form (080478-FOR) [\(Section 14.8\)](#) to Ipsen according to the timelines set out in section 8.2.2.

8.2.2 REPORTING OF SAFETY REPORTS

In order to adhere to all applicable laws and regulations for reporting of a safety report, the Investigator should notify to the sponsor and sponsor will notify Ipsen within 24 hours of the study site staff becoming aware of the safety report. It is the Investigator's responsibility to ensure that the reporting information and procedures are used and followed appropriately.

Reporting Information for safety reports

To report initial or follow-up information to Ipsen, a completed ***Clinical Study Serious Adverse Event (SAE) report form (080478-FOR)*** should be sent to the following within 24 hours of becoming aware of the event:

[name], Local Pharmacovigilance Manager

Email: [contact], [contact]

[contact] / [name]

[contact]

All adverse events will be processed by Ipsen according to their relevant Standard Operating Procedures. This includes the follow up of adverse event reports with the Investigator, as required.

If an AE occurs with a "non Ipsen product", the Investigator should consider informing the competent authority in the Member State where the event occurred or to the marketing authorisation holder of the suspected medicinal product, but not to both (to avoid duplicate reporting).

8.2.3 MANDATORY INFORMATION FOR REPORTING AN ADVERSE EVENT

The following information is the minimum that must be provided to Sponsors and will be provided to Ipsen's Pharmacovigilance contact within 24 hours for each adverse event:

- Patient identifier
- Product name
- Adverse Event description including assessment of causal relationship and seriousness
- Investigator name and contact details

The additional information included in the adverse event report form must be provided to Ipsen as soon as it is available.

The investigator should report a diagnosis or a syndrome rather than individual signs or symptoms. The investigator should also try to separate a primary adverse event considered as the foremost untoward medical occurrence from secondary adverse events which occurred as complications. The investigator should also provide the batch number and expiry date of the concerned product wherever possible.

8.3 SAFETY CLASIFICATIONS

8.3.1 RELATIONSHIP OF EVENTS TO THE MEDICINAL PRODUCT

The following definitions should be considered when evaluating the relationship of AEs and SAEs to the study treatment:

| Relationship of Event to Study Treatment | |
|--|--|
| Not related | An adverse event will be considered “not related” to the use of the medicinal drug if there is not a possibility that the event has been caused by the product under investigation. Factors pointing toward this assessment include, but are not limited to: the lack of reasonable temporal relationship between administration of the drug and the event, the presence of a biologically implausible relationship between the product and the adverse event (e.g., the event occurred before administration of drug), or the presence of a more likely alternative explanation for the adverse event. |
| Related | An adverse event will be considered “related” to the use of the medicinal drug if there is a possibility that the event may have been caused by the product under investigation. Factors that point toward this assessment include, but are not limited to: a positive rechallenge, a reasonable temporal sequence between administration of the drug and the event, a known response pattern of the suspected drug, improvement following discontinuation or dose reduction, a biologically plausible relationship between the drug and the adverse event, or a lack of an alternative explanation for the adverse event |

8.3.2 SEVERITY OF EVENTS

The following definitions should be considered when evaluating the severity of oncology events:

| Severity of Events | |
|--------------------|--------------------------------------|
| Grade | Definition |
| 1 | Mild adverse event |
| 2 | Moderate adverse event |
| 3 | Severe and undesirable adverse event |

Sponsor's code: ACTION
EudraCT No: 2019-004991-20
Version: 4.0
Date: 15 July 2021
CONFIDENTIAL

| | |
|---|---|
| 4 | Life-threatening or disabling adverse event |
| 5 | Death related to adverse event |

8.3.3 EXPECTEDNESS OF EVENTS

Expectedness of all AEs will be determined by Ipsen according to the SmPC.

8.3.4 SAFETY DATA LISTING

A safety data listing will be obtained from the global safety database and will be included in the clinical study report.

All collected adverse events will be summarized for inclusion as part of any interim safety analysis and in the clinical study report.

9. STATISTICAL METHODS

9.1 END-POINTS

The study will be analyzed using standard statistical methods to estimate rates and 95%CI (for ORR and other binary variables) by means of the Clopper-Pearson exact method, and the Kaplan-Meier method to describe the survival functions and the median and [95%CI]. Indirect comparisons with will conducted with external data by assessing the 95%CI of the study estimates. A Statistical Analysis Plan, which will include all details regarding all analyses, the interim method, the handling of missing data and any plan for the analysis, will be finalized before the initiation of the study recruitment.

Primary Outcome(s)

- Rate of adverse events (AE) with Common Terminology Criteria for Adverse Events (CTCAE)≥3 excluding palmar-plantar erythrodysthesia, rate of AEs, rate of related-AEs and rate of death. Rate of AEs leading to treatment discontinuation.
- Adverse events will be graded following version 5.0 of the CTCAE of the National Cancer Institute, during treatment and 30 days after the last dose.

Secondary Outcome(s)

Time to progression, objective response rate, pattern of progression, overall survival, post-progression survival, rate of patients who develop new extrahepatic spread. Serum and tissue marker characterization.

Safety Outcomes

This is a clinical trial were the main purpose is the assessment of safety, therefore, the primary and secondary outcomes were defined accordingly, as described above.

9.2 SAMPLE SIZE

The sample size calculation will be triggered by the primary outcome, i.e, the rate of adverse events (AE) with CTCAE \geq 3 excluding palmar-plantar erythrodysthesia (critical AEs). The expected rate for this outcome was 56% in this population¹. The Simon's two-stage optimal design² will be used to test the alternative hypothesis that with cabozantinib the rate of critical AEs will be reduced at least to 32.5% against the null hypothesis of 56% as previously observed. In the first stage, 14 patients will be accrued. If there are 8 or more critical AEs in these 14 patients, the study will be stopped because of futility. Otherwise, 26 additional patients will be accrued for a total of 40. The null hypothesis will be rejected if 23 or fewer critical AEs are observed in 40 patients. This design yields a type I error rate of 2.5% one-sided and power of 80% when the true response rate is 67.5%.

All patients exposed to the study treatment (regardless of protocol adherence) will count be safety, and thus no need to sample size increases as per potential withdrawals are foreseen.

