The sample size calculation will be triggered by the primary outcome, i.e, the rate of adverse events (AE) with CTCAE≥3 excluding palmar-plantar erythrodysthesia (critical AEs). The expected rate for this outcome was 56% in this population. The Simon's two-stage optimal design will be used to test the alternative hypothesis that with cabozantinib the rate of critical AEs will be reduced at least to 32.5% against the null hypothesis of 56%. In the first stage, 14 patients will be accrued and if there are 8 or more critical AES in these 14 patients, the study will be stopped for futility. Otherwise, 26 additional patients will be accrued for a total of 40. The null hypothesis will be rejected if 23 or fewer critical AEs are observed in 40 patients. This design yields a type I error rate of 2.5% one-sided and power of 80% when the true response rate is 67.5%.

Planned Study Timelines:

1. Enrolment rate (patients per month): 3
2. Planned estimate of treatment(s) duration: **24months**
3. Submission date to health authority/ethics: Jan 2020
4. Start of subject enrolment: March 2020
5. End of Subject enrolment: Jul 2022
6. All patients completed: **Oct 2023**
7. End of Study: Jan 2024
8. Report: **Q2-Q3 2024**
9. Planned publication/presentation: Q1 2025

TABLE OF CONTENTS.

| | |
|--|-----------|
| TITLE PAGE | 1 |
| SYNOPSIS | 2 |
| 1. INTRODUCTION | 13 |
| 1.1 HEPATOCELLULAR CARCINOMA | 13 |
| 1.2 CABOZANTINIB: BACKGROUND | 13 |
| 1.2.1 PHARMACOLOGY AND PHARMACOKINETICS..... | 13 |
| 1.2.2 CABOZANTINIB SAFETY SUMMARY IN PATIENTS WITH HEPATOCELLULAR CARCINOMA..... | 16 |
| 1.2.3 SUMMARY OF CABOZANTINIB CLINICAL ACTIVITY IN HEPATOCELLULAR CARCINOMA..... | 16 |
| 1.2.4 RATIONALE FOR THE CURRENT STUDY | 17 |
| 1.2.4.1 TREATMENT SCHEDULE | 17 |
| 2. STUDY OBJECTIVES..... | 17 |
| 3. ETHICAL CONSIDERATIONS..... | 17 |
| 3.1 GOOD CLINICAL PRACTICE | 17 |
| 3.2 INSTITUTIONAL REVIEW BOARD/INDEPENDENT ETHICS COMMITTEE | 18 |
| 3.3 INFORMED CONSENT..... | 18 |
| 4. STUDY DESIGN AND PLAN | 19 |
| 4.1 TREATMENT PLAN..... | 19 |
| 4.1.1 SCREENING PHASE | 19 |
| 4.1.2 CABOZANTINIB..... | 20 |
| 4.1.3 END OF THE STUDY | 20 |
| 4.1.4 DISCONTINUATION OF CABOZANTINIB..... | 21 |
| 4.1.5 POST STUDY DRUG STUDY FOLLOW-UP..... | 21 |
| 4.1.6 WITHDRAWAL OF CONSENT | 21 |
| 4.1.7 LOST TO FOLLOW-UP | 22 |
| 5. PATIENT POPULATION..... | 22 |
| 5.1 INCLUSION CRITERIA..... | 22 |
| 5.1.1 SIGNED WRITTEN INFORMED CONSENT | 22 |
| 5.1.2 TARGET POPULATION | 22 |

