7.4 JUSTIFICATION OF SAMPLE SIZE

The sample size calculation will be triggered by the primary outcome, i.e, the rate of adverse events (AE) with CTCAE ≥ 3 excluding palmar-plantar erythrodysthesia (critical AEs). The expected rate for this outcome was 56% in this population^{Error! No se encuentra el origen de la referencia.}. The Simon's two-stage optimal design¹¹ will be used to test the alternative hypothesis that with cabozantinib the rate of critical AEs will be reduced at least to 32.5% against the null hypothesis of 56% as previously observed. In the first stage, 14 patients will be accrued. If there are 8 or more critical AES in these 14 patients, the study will be stopped because of futility. Otherwise, 26 additional patients will be accrued for a total of 40. The null hypothesis will be rejected if 23 or fewer critical AEs are observed in 40 patients. This design yields a type I error rate of 2.5% one-sided and power of 80% when the true response rate is 67.5%.

All patients exposed to the study treatment (regardless of protocol adherence) will count be safety, and thus no need to sample size increases as per potential withdrawals are foreseen.

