- Symptom scales

- Fatigue, FATI
- Body image BI
- Jaundice, JAUN
- Nutrition, NUTR
- Pain, PA
- Fever, FEV
- Single items
 - Abdominal swelling, AB
 - Sex life, SX

The individual items will be described as a continuous and as a categorical variable (see section 8.6.1) by time-point.

The scale scores will be also described as a continuous variable and the MMRM will be applied.

8.6.5.3.7

Adverse events

A summary of treatment-emergent adverse events (AEs), including the number of events reported, the number and percentage of patients reporting at least one event of each of the following:

- Any AE
- Any severe AE (grade greater or equal to 3 in the NCI CTCAE v5.0)
- Any AEs (CTCAE) ≥ 3 excluding palmar-plantar erythrodysthesia
- Any treatment-related AE (with cabozantinib)
- Any severe treatment-related AE
- Any AE with outcome of death
- Any serious AE
- Any treatment-related serious AE
- Any AE leading to discontinuation of the treatment permanently (cabozantinib)
- Any treatment-related AE leading to discontinuation of the treatment permanently (regorafenib, nivolumab or both)

The number and percentage of patients who experience one or more treatment-emergent AEs as well as the number of AE episodes will be tabulated by body system, preferred term (according to MedDRA v21.1), seriousness, intensity, action taken, outcome, relationship to the study drug and NCI CTCAE v5.0.

8.6.5.3.8

Concomitant medication

The concomitant medication after randomization will be described by time-point and study product. Concomitant medication and its characteristics will be listed. The number of patients with at least concomitant medication globally and by ATC code (according to ATC classification index with the last version of WHO-DD at the end of last patient follow-up) will be described.

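### The printed go/no-go limits (8 of 14, 23 of 40) do not have the stated 2.5% and 80%: AE-free counts are printed as critical-AE counts, and the unit is events rather than patients

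*Protocol*

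**What the plan says.** Protocol 9.2 sizes the trial on the rate of AEs of CTCAE grade 3 or higher, excluding palmar-plantar erythrodysesthesia, which it calls critical AEs. The null is "The expected rate for this outcome was 56% in this population". The alternative is that "the rate of critical AEs will be reduced at least to 32.5% against the null hypothesis of 56% as previously observed". A Simon two-stage optimal design is named: "In the first stage, 14 patients will be accrued", then 26 more for a total of 40.

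The decision limits are:
- Stage 1: "If there are 8 or more critical AEs in these 14 patients, the study will be stopped because of futility".
- Final: "The null hypothesis will be rejected if 23 or fewer critical AEs are observed in 40 patients".

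The section attaches a one-sided type I error of 2.5% and power of 80% at a true response rate of 67.5%. The Synopsis has the same stage-1 limit ("if there are 8 or more critical AES in these 14 patients, the study will be stopped for futility"), as does SAP 7.4 ("If there are 8 or more critical AES in these 14 patients"), and both repeat the final limit of 23.

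Elsewhere the endpoint is treated per patient. SAP 8.6.5.1 lists it among the binary variables, with Clopper-Pearson intervals. SAP 8.6.5.3.7 plans an AE summary "including the number of events reported, the number and percentage of patients reporting at least one event" in each category, so it reports both units. Protocol 7.2.1 says AEs are documented event by event. No section links the patient-level definition to the two limits.

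**The concern.** The final limit looks wrong on sight. Under the null, 40 × 0.56 = 22.4 affected patients are expected, and the plan would reject the null at 23 or fewer. An observed rate of 23/40 = 57.5% is above the null rate, yet it would be declared a reduction.

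The unit is also loose. A Simon design needs one yes/no outcome per patient, and one patient can have several grade 3 or higher AEs, so a count of AEs in 14 or 40 patients is not binomial.

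These limits are the only formal interim stopping rule and the only stated criterion for rejecting the null. Protocol section 2 and SAP 6.3 also make the exploratory work conditional on meeting the safety endpoint.

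**Working it through.** **Inputs** (Protocol 9.2): critical-AE rate q = 0.56 under the null and 0.325 under the alternative; stage 1 n = 14; total n = 40; one-sided alpha 2.5%; power 80%. The AE-free rates are the complements: 1 − 0.56 = 0.44 and 1 − 0.325 = 0.675. The second is the 67.5% response rate in the text, so the response in this design is being free of a critical AE.

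**Step 1: find the design behind the stated figures.** A search for Simon's optimal design with p0 = 0.44, p1 = 0.675, alpha ≤ 0.025 and power ≥ 0.80 returns n1 = 14, r1 = 7, n = 40, r = 23, with type I error 2.39% and power 80.04%. All four integers match the protocol. In this design r1 and r count AE-free patients: stop if 7 or fewer of 14 are AE-free, and reject the null only if more than 23 of 40 are AE-free.

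**Step 2: convert to affected patients.**
- Stage 1: AE-free ≤ 7 means affected ≥ 14 − 7 = 7. Stop if 7 or more of 14.
- Final: AE-free ≥ 24 means affected ≤ 40 − 24 = 16. Reject if 16 or fewer of 40.

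The printed 8 is the AE-free count needed to continue, used as the AE count for stopping. The printed 23 is the largest AE-free count that fails to reject, used as the largest AE count that rejects.

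**Step 3: operating characteristics when patients are counted.** Let a1 be the largest stage-1 count that continues and a the largest final count that rejects. Then

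P(reject) = Σ (x = 0 to a1) Bin(x; 14, q) × P[Bin(26, q) ≤ a − x]

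| Rule (affected patients) | a1, a | Type I error (q = 0.56) | Power (q = 0.325) |
|---|---|---|---|
| As printed: stop ≥ 8, reject ≤ 23 | 7, 23 | 36.1% | 95.0% |
| Only final limit restated: stop ≥ 8, reject ≤ 16 | 7, 16 | 2.82% | 85.7% |
| Both restated: stop ≥ 7, reject ≤ 16 | 6, 16 | 2.39% | 80.04% |

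Under the null, the chance of stopping at stage 1 is 57.6% with the printed limit and 76.6% with the restated one. If the printed stage-1 stop were ignored, the type I error would be 63.5%.

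**Step 4: printed limits read literally as event counts.** The documents do not give the number of critical AEs per affected patient, m. Assume that each affected patient has 1 + Poisson(m − 1) events. Simulated results (200,000 trials per cell) for stop ≥ 8 and reject ≤ 23 events:

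| m | Type I error | Power | Stage-1 stop at q = 0.325 |
|---|---|---|---|
| 1.1 | 21% | 88% | 11% |
| 1.2 | 12% | 81% | 18% |
| 1.25 | 8% | 77% | 22% |
| 1.5 | 1.8% | 56% | 38% |
| 2.0 | 0.1% | 23% | 63% |

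No row gives 2.5% and 80% together.

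**The case against.** The strongest reply is that the intent is per patient and a competent analyst would see it. The design is binomial, and the 67.5% response rate only makes sense per patient. SAP 8.6.5.1 calls the endpoint binary, SAP 8.6.5.3.7 reports patients with at least one event for exactly this category, and SAP 7.5 assigns the interim to an independent statistician. This stands, and it makes the unit the lesser defect. It does not rescue the limits: the per-patient reading is the one that gives a 36.1% type I error.

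A reader might infer that counting events is what costs the design its error rates, or that it destroys the 80% power. The documents do not support either. The printed limits never had those rates. Under event counting, power is still about 81% at 1.2 events per affected patient and falls well short only nearer 1.5, and the documents give no value for that number. Event counting also lowers the type I error of the printed limits. Nor does any section show that events would be used: the interim report's AE list by subject (SAP 7.5) serves a patient count equally well.

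Finally, SAP 8.5 labels the primary endpoints non-confirmatory and SAP 8.6 plans no inferential analysis. That softens the weight of the final test, but SAP 7.4 keeps the rejection rule and SAP 7.5 applies the stage-1 limit to decide whether the trial continues.

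**Conclusion.** The concern holds. As printed in all three places, the limits do not deliver the stated 2.5% and 80%. Counted per patient, they give 36.1% and 95.0%, results that are exact and need only the protocol's own rates and sample sizes. The main cause is that AE-free boundaries are printed as AE counts. That cause is inferred, but the optimal design for the stated inputs reproduces all four numbers. The secondary cause is the undefined unit; its size rests on the 1 + Poisson assumption and on a number of events per patient that is not in the documents, so only the range in the working can be given.

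The two defects need correcting together. Naming the patient as the unit and keeping 8 and 23 leaves a 36.1% type I error. Changing only the final limit leaves 2.8%, still above 2.5%. The 2.39% for the restated limits assumes that the stage-1 stop is observed; if it were ignored, the type I error would be 3.05%.

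**What to change.** Make the same change in the Synopsis, Protocol 9.2 and SAP 7.4:
- Define the count as the number of patients with at least one critical AE (CTCAE grade 3 or higher, excluding palmar-plantar erythrodysesthesia).
- Stage 1: stop if 7 or more of the 14 patients are affected.
- Final: reject the null if 16 or fewer of the 40 patients are affected.
- Report the exact type I error (2.39%) and power (80.04%), and say that the 67.5% response rate is the AE-free rate.

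In SAP 7.5, state that the interim report applies the rule to patients, not events.

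The cost is an amendment to the wording of both documents. Sample size, visits and data collection do not change.

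### The Simon boundaries are counts of AE-free patients relabelled as critical AEs, so the success rule (23 or fewer of 40) has a type I error of about 36%, not 2.5%

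*Protocol*

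**What the plan says.** Protocol 9.2 sets up a one-sided test that "the rate of critical AEs will be reduced at least to 32.5% against the null hypothesis of 56% as previously observed", using "The Simon's two-stage optimal design".

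- **Stage 1:** "If there are 8 or more critical AEs in these 14 patients, the study will be stopped because of futility".
- **Stage 2:** "Otherwise, 26 additional patients will be accrued for a total of 40".
- **Success:** "The null hypothesis will be rejected if 23 or fewer critical AEs are observed in 40 patients".
- **Claimed properties:** "This design yields a type I error rate of 2.5% one-sided and power of 80% when the true response rate is 67.5"%.

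The Synopsis and SAP 7.4 give the same boundaries and the same claimed properties. Neither document has a corrected version elsewhere.

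**The concern.** The contradiction shows before any calculation. A test meant to demonstrate a reduction from 56% declares success at 23/40 = 57.5%, above the null rate. No one-sided 2.5% test of a reduction can do that.

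The paragraph also mixes two scales. The hypotheses and both boundaries are in critical AEs, while the power is quoted at a response rate of 67.5%, which is 100% − 32.5%, the AE-free rate under the alternative.

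This is the only numerical decision rule in the trial. SAP 7.5 requires the interim report to draw its conclusions from the SAP 7.4 stopping rule. Protocol 2 and 7.4 and SAP 6.3 make the follow-on exploratory study conditional on meeting the safety endpoint. As written, a treatment no safer than the reference could be declared a success.

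A lesser point is that the rule counts critical AEs, not patients with at least one. One patient can have several events, and event counts are not binomial.

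**Working it through.** **Inputs (Protocol 9.2).** Critical-AE rate 56% under the null and 32.5% under the alternative; 14 patients in stage 1, 26 more in stage 2, 40 in total; stop at 8 or more of 14; reject at 23 or fewer of 40; one-sided type I error 2.5%; power 80%. The unit is taken to be a patient with at least one critical AE.

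**Step 1: reproduce the stated design.** On the AE-free scale, p0 = 1 − 0.56 = 0.44 and p1 = 1 − 0.325 = 0.675. An exhaustive search for the Simon optimal design with type I error ≤ 0.025 and power ≥ 0.80 returns n1 = 14, r1 = 7, n = 40, r = 23. Its attained type I error is 0.0239, its power 0.8004 and its expected sample size under the null 20.1. These are the plan's sizes and its 23, and the plan's 8 is r1 + 1.

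**Step 2: compare the decisions attached to the same numbers.**

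| Count | Reproduced design (AE-free patients) | Plan (critical AEs) |
|---|---|---|
| 8 or more of 14 | continue | stop |
| 23 or fewer of 40 | do not reject the null | reject the null |

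Taking complements properly:

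- 7 or fewer AE-free of 14 is 14 − 7 = 7 or more with a critical AE: stop.
- 24 or more AE-free of 40 is 40 − 24 = 16 or fewer with a critical AE: reject.

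**Step 3: evaluate the rule as written.** If the trial stops at s or more of 14 and rejects at m or fewer of 40, then

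P(reject | p) = Σ over a = 0, …, s − 1 of P(Bin(14, p) = a) × P(Bin(26, p) ≤ m − a).

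With s = 8, m = 23 and p = 0.56:

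| a | P(Bin(14, 0.56) = a) | P(Bin(26, 0.56) ≤ 23 − a) | Product |
|---|---|---|---|
| 0 | 0.00001 | 0.99994 | 0.00001 |
| 1 | 0.00018 | 0.99958 | 0.00018 |
| 2 | 0.00150 | 0.99796 | 0.00150 |
| 3 | 0.00765 | 0.99237 | 0.00759 |
| 4 | 0.02677 | 0.97701 | 0.02615 |
| 5 | 0.06815 | 0.94250 | 0.06423 |
| 6 | 0.13011 | 0.87812 | 0.11425 |
| 7 | 0.18925 | 0.77695 | 0.14704 |

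The products sum to 0.361. The same formula gives 0.950 at p = 0.325, 0.224 at p = 0.60 and 0.095 at p = 0.65.

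**Step 4: compare candidate rules.**

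| Stop at (of 14) | Reject at (of 40) | Type I error | Power | Stage 1 stop under the null |
|---|---|---|---|---|
| ≥ 8 | ≤ 23 (as written) | 36.1% | 95.0% | 57.6% |
| ≥ 7 | ≤ 16 (complement) | 2.39% | 80.04% | 76.6% |
| ≥ 8 | ≤ 16 | 2.82% | 85.7% | 57.6% |
| ≥ 8 | ≤ 15 | 1.35% | 78.7% | 57.6% |

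Correcting only the final boundary leaves the type I error above 2.5%.

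**Step 5: if the stage 1 stop is not enforced.** P(Bin(40, 0.56) ≤ 23) = 63.5% and P(Bin(40, 0.56) ≤ 16) = 3.05%.

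**The case against.** The strongest reply is that the final test may never be run. SAP 8.6 describes the analysis as non-inferential, SAP 8.5 labels the primary endpoints non-confirmatory, and SAP 8.6.5.1 reports only rates with Clopper-Pearson intervals. Protocol 9.1 makes external comparisons through the 95% interval. At 23/40 that interval is 40.9% to 73.0%, which includes 56%, so a reader of the planned output would not see an improvement. The documents also never say that meeting the safety endpoint means passing the Simon rule, so its role as the gate to the follow-on study is inferred. And only one successful count, 23, lies above the null; 22/40 is 55%.

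These points limit the consequence but leave the error in place. SAP 7.4 keeps the test and its claimed properties. SAP 7.5 applies the stage 1 boundary, which is also wrong, and Protocol 10.2 has the data safety monitoring board's recommendation guided by monitoring boundaries. No other numerical criterion for the safety endpoint is given.

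Two further objections stand as refinements:

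- Every two-stage figure assumes an enforced stage 1 stop, yet Protocol 10.2 makes the board's output a recommendation for the sponsor to assess.
- The events-versus-patients problem is one of wording in the rule. SAP 8.6.5.1 already treats the endpoints as binary, and SAP 8.6.5.3.7 counts patients with at least one event.

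**Conclusion.** The concern holds. As written, the rule has a type I error of 36.1% against the stated 2.5%, and a power of 95.0% against the stated 80%. Its success limit lies above the null rate. These figures assume that patients are the unit and that the stage 1 stop is enforced; without the stop, the type I error is 63.5%.

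That the boundaries were relabelled from the AE-free scale is an inference, but a firm one: the search on that scale returns the plan's 14, 40 and 23, with its 8 equal to r1 + 1. The type I error of the rule as written does not depend on that inference. The SAP leaves unclear whether the final test will be performed formally. This must be fixed, because the stage 1 boundary is used at the interim and the final rule is the only stated criterion for success.

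**What to change.** In the Synopsis, Protocol 9.2 and SAP 7.4, replace both boundaries: stop if 7 or more of the first 14 patients have at least one critical AE; reject the null if 16 or fewer of 40 patients have at least one. State the exact properties (type I error 2.39%, power 80.04%), say that they assume a binding stage 1 stop, and express the power at a critical-AE rate of 32.5%. State in the SAP whether the test is to be performed, and whether it defines meeting the safety endpoint.

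The documents do not say whether stage 1 is complete. If it has been run at 8 or more, keep that boundary, set the final limit at 15 or fewer of 40, and report type I error 1.35% and power 78.7%, slightly below the planned 80%. The trial is open-label, so the amendment should record that the new limit follows from the original design parameters and not from the accrued counts.

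The cost is a protocol amendment and a SAP update. No patients or procedures are added. The success criterion becomes stricter, as the design intended.
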